8.1 Efficacy assessments

Planned time points for all efficacy assessments are provided in the SoA.

8.1.1 Ophthalmology assessments

Unless specified otherwise, ophthalmology examinations will be done for both eyes.

Source data of all ophthalmology examinations will be archived at the site. This includes data and images sent to the central reading center for evaluation.

8.1.1.1 Color fundus photography (CFP)

The anatomical state of the retinal vasculature will be evaluated by an ophthalmologist from posterior segment (Section 8.1.1.6) examination and CFP. All digital CFP images need to be taken by a certified technician following an acquisition protocol for ETDRS 7-Fields of the central reading center at the visits indicated in the SoA.

All CFPs will be transmitted to the **central reading center** for ETDRS diabetic retinopathy severity scale (DRSS, Table 8-1) grading and storage. The images of the screening visit of both eyes will be used as part of the eligibility assessment regarding the severity of diabetic retinopathy.

CFPs may, in addition, be evaluated for additional, exploratory, endpoints. This may include assessment of microaneurysm turnover (Nunes et al. 2009) or measurement of diameters of retinal vessels as described previously (Lundberg et al. 2013). This may involve transmission of CFP to additional central reading centers.

Table 8-1 ETDRS final retinopathy severity scale (for individual eyes)

Level	Severity
10	DR absent
20	Microaneurysms only
35	Mild NPDR
43	Moderate NPDR
47	Moderately severe NPDR
53	Severe NPDR
61	Mild PDR
65	Moderate PDR
71	High-risk PDR
75	High-risk PDR
81	Advanced PDR: fundus partially obscured, center of macula attached
85	Advanced PDR: posterior fundus obscured, or center of macula detached
90	Cannot grade, even sufficiently for level 81 or 85

ETDRS = Early Treatment Diabetic Retinopathy Study; DR = diabetic retinopathy; NPDR = non-proliferative DR; PDR = proliferative DR; Modified from (Staurenghi et al. 2018)

09 FEB 2023 Page: 49 of 95

8.1.1.2 Best corrected visual acuity (BCVA)

Visual function will be assessed using a modified ETDRS protocol starting at 4 meters (AREDS 1999). Visual Acuity examiners must be certified to ensure consistent measurement of BCVA.

8.1.1.3 Fluorescein angiography (FA)

The anatomical state of the retinal vasculature of the study eye (transit eye) and the fellow eye (non-transit eye) will be evaluated by FA. All FAs will be conducted by a certified technician following an acquisition protocol of the reading center. The angiographic images will be evaluated by a study ophthalmologist for individual safety decisions, and by the central reading center to support the DRSS assessment. All FA images will be sent to the central reading center for evaluation.

At screening a standardized set of FA images with the study eye as transit eye will be sent to the reading center for evaluation and eligibility assessment.

8.1.1.4 Optical coherence tomography (OCT)

Structural OCT will be performed preferably by using spectral domain devices. The specific device models accepted for the study will be defined by the reading center. OCTs will be performed by certified technicians following an acquisition protocol of the reading center as scheduled in the SoA for local safety assessment. Newly found clinically relevant pathologies should be reported as adverse event. All obtained images will be sent to the reading center for evaluation at the visits stated in the SoA.

At screening a standardized set of OCT images will be sent to the reading center for evaluation and eligibility assessment.

OCT Central Subfield Thickness (CST) will be analyzed by the reading center to guide the investigator relating to Exclusion criterion 6, which excludes participants with macular edema requiring treatment. The thresholds depend on gender ($\pm 15~\mu m$ in men) and on the inclusion or exclusion of Bruch's membrane by the OCT-devices segmentation algorithm.

The reference threshold for the CST will be determined by the central reading center using the Heidelberg-Engineering segmentation algorithm as a standard, which includes Bruch's membrane. For other OCT-devices, equivalent CST values will be provided by the central reading center.

The CST thresholds used are:

• $\geq 305 \, \mu \text{m}$ in women, $\geq 320 \, \mu \text{m}$ in men

8.1.1.5 Optical coherence tomography angiography (OCT-A)

For Part 1, OCT-A is mandatory, for Part 2, OCT-A is optional. In any case, the OCT-A needs to be performed by a certified technician following an acquisition protocol of the reading center as scheduled in the SoA. The specifications of this OCT-A can be found in the acquisition protocol of the Reading center. Images obtained via OCT-A will be sent to the Central Reading Center for evaluation.

09 FEB 2023 Page: 50 of 95

The following parameters will be quantified and assessed prior to start of treatment with the study intervention, after the first study intervention administration and at steady state treatment with each of the dose levels as shown in the SoA (Section 1.3). For the following vascular regions in the central 3 mm x 3 mm will be assessed separately to the extent feasible:

- Superficial retinal layer
- Intermediate retinal layer
- Deep retinal layer
- Retina (cumulative, all layers combined)

The following parameters will be assessed for these vascular regions, as applicable:

- Perfusion density
- Vessel density
- Foveal avascular zone

Cross-sectional macular full depth line scans acquired with an experimental software used for positioning the scan lines and to average the information obtained for each scan will be analyzed for

- Total perfusion
- Vessel density

8.1.1.6 Slit lamp biomicroscopy (anterior and posterior segment)

The slit lamp examination (anterior and posterior segment) will be performed according to local medical practice and applicable medical standards at the site as stated in the SoA. Abnormal findings are to be recorded in the eCRF as either medical history or adverse event as applicable.

8.1.1.7 Tonometry (intraocular pressure (IOP) measurement)

Intraocular pressure is to be measured with any locally approved non-contact tonometer.

In case that there is no non-contact tonometer available at the site, applanation tonometry (Goldmann, Tonopen or other locally approved alternatives) may be used. In any case, where both methods are available the non-contact method is to be used

The same method of IOP measurement must be used throughout the study for each individual participant. Values and measuring type are to be recorded in the eCRF.

8.1.2 Vision-threatening complications

Vision-threatening complications are defined as occurrence of any of the following adverse events:

- PDR
- Any ocular neo-vascularization

09 FEB 2023 Page: 51 of 95

- Center-involved (ci) (central ETDRS subfield) DME
- Drop of BCVA of 10 letters or more from baseline

The assessment will be continued after treatment discontinuation if possible.

Treatment of the vision threatening complication should follow local standards and guidelines, i.e. treatment of ci DME with anti-VEGF or other appropriate measures, at the discretion of the investigator.

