In previous studies of intra-vitreal anti-VEGF treatments, 2-step DRSS improvements were detected as early as 8 weeks after treatment initiation and reached a maximum after 6 to 12 months of treatment. However, recent clinical trials of oral agents in NPDR failed after treatment periods of up to 24 weeks (e.g. NCT03238963). Therefore, the primary endpoint assessment is planned after 48 weeks of treatment. Additional assessments are planned for DRSS assessment at 12 and 24 weeks of treatment.

09 FEB 2023 Page: 30 of 95

Assessment of vision threatening complications as secondary endpoint is planned in addition, to correlate the DRSS-change with a clinical outcome parameter in support of the efficacy assessment in this study.

Participant input into design

A patient advisory board was conducted to

- Identify potential hurdles in the plans for the clinical trial to recruitment, adherence with the study procedures, and patient retention
- Confirm the relevance of the investigated endpoints for patients with diabetic retinopathy (DR)
- Seek input on medical need and relevant study outcomes in NPDR from the perspective of patients with DR

The feedback from the advisory board was duly integrated in the study protocol.

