9.4 Statistical analyses

The statistical analysis plan will be finalized prior to unmasking and it will include a more technical and detailed description of the statistical analyses described in this section. This section is a summary of the planned statistical analyses of the most important endpoints including primary and key secondary endpoints.

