9.4.3 Secondary endpoint(s)

9.4.3.1 Efficacy

The secondary endpoints for primary objective (efficacy) of study are

09 FEB 2023 Page: 63 of 95

• "\ge 2step improvement in DRSS in the study eye" at 24 weeks of treatment: These endpoints will be analyzed descriptively with a similar methodology described for the primary endpoints.

• Vision-threatening complications in study eye up to 48 weeks of treatment. These endpoints will be analyzed by the Kaplan-Meier-method. Participants dropping out from the study without a vision-threatening complication will be censored at the last visit with evidence of no event.

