10.3.1 Definition of AE

AE definition

- An AE is any untoward medical occurrence in a clinical study participant, associated with the use of study intervention, whether or not considered related to the study intervention.
- NOTE: An AE can therefore be any unfavorable and unintended sign (including an abnormal laboratory finding), symptom, or disease (new or exacerbated) associated with the use of study intervention.

Events meeting the AE definition

- Any abnormal laboratory test results (hematology, clinical chemistry, or urinalysis) or other safety assessments (e.g. ECG, radiological scans, vital signs measurements), including those that worsen from baseline, considered clinically significant in the medical and scientific judgment of the investigator (i.e. not related to progression of underlying disease).
- Exacerbation of a chronic or intermittent pre-existing condition including either an increase in frequency and/or intensity of the condition.
- New conditions detected or diagnosed after study intervention administration even though it may have been present before the start of the study.
- Signs, symptoms, or the clinical sequelae of a suspected intervention-intervention interaction.
- Signs, symptoms, or the clinical sequelae of a suspected overdose of either study intervention or a concomitant medication. Overdose per se will not be reported as an AE/SAE unless it is an intentional overdose taken with possible suicidal/self-harming intent. Such overdoses should be reported regardless of sequelae.

Events NOT meeting the AE definition

- Any clinically significant abnormal laboratory findings or other abnormal safety assessments which are associated with the underlying disease, unless judged by the investigator to be more severe than expected for the participant's condition.
- The disease/disorder being studied or expected progression, signs, or symptoms of the disease/disorder being studied, unless more severe than expected for the participant's condition.
- Medical or surgical procedure (e.g. endoscopy, appendectomy): the condition that leads to the procedure is the AE.
- Situations in which an untoward medical occurrence did not occur (social and/or convenience admission to a hospital).
- Anticipated day-to-day fluctuations of pre-existing disease(s) or condition(s) present or detected at the start of the study that do not worsen.

09 FEB 2023 Page: 73 of 95

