#### Vision-threatening complications at 12, 24, 48 Weeks of treatment in the study eye

Assessment of VTC as secondary endpoint is planned in addition, to correlate the DRSSchange with a clinical outcome parameter in support of the efficacy assessment in this study. VTC are defined as occurrence of any of the following AEs:

- PDR (DRSS  $\geq 61$ )
- Any ocular neo-vascularization (retinal or anterior-segment neovascularization)
- Center-involved (central ETDRS subfield) DME
- Drop of BCVA of 10 letters or more from baseline

Study investigations may be continued after treatment discontinuation, after investigator assessment. Treatment of the VTC should follow local standards and guidelines, at the discretion of the investigator.

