#### Vision-threatening complications at 12, 24, 48 Weeks of treatment in the study eye

VTC will be recorded continuously during the study. Predefined timepoints for assessment are 12, 24, and 48 weeks of treatment. VTC are recorded separately for the study eye and the fellow eye. Separate assessments will be done for the study eye and across both eyes (timepoint when a VTC appears in any eye). These endpoints will be analyzed by the Kaplan-Meier-method on the PPS and in addition, as a sensitivity analyses on the FAS. Confidence intervals will be provided for probability of having a vision threatening event up to these time points. Participants dropping out from the study without a VTC will be censored at the last visit. Furthermore, if deemed necessary, the endpoint VTC in any eye (yes/no) will be analyzed using the same Bayesian analysis described for the primary efficacy endpoint (see Section 4.2.2) on the PPS.

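### Vision-threatening complications are counted through adverse-event records that the AE definition can exclude, and the SAP drops the protocol's censoring condition without declaring it

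*Protocol*

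**What the plan says.** Protocol 8.1.2 lists four components: PDR, any ocular neovascularisation, centre-involved DME, and a visual acuity loss of at least 10 letters. It introduces them with "Vision-threatening complications are defined as occurrence of any of the following adverse events". SAP 4.3.1.1 keeps the basis ("VTC are defined as occurrence of any of the following AEs"), but ties PDR to DRSS 61 or above and specifies neovascularisation as retinal or anterior-segment.

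Protocol 10.3.1 lists among events that do not meet the AE definition: "The disease/disorder being studied or expected progression, signs, or symptoms of the disease/disorder being studied, unless more severe than expected for the participant's condition".

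On rank, Protocol 4.2 states: "Assessment of vision threatening complications as secondary endpoint is planned in addition". Its purpose there is to relate DRSS change to a clinical outcome.

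For the Kaplan-Meier analysis, Protocol 9.4.3.1 says that dropouts without an event "will be censored at the last visit with evidence of no event". SAP 4.3.1.2 says: "Participants dropping out from the study without a VTC will be censored at the last visit". SAP 4.8, on changes to the planned analyses, mentions only the removal of serum lipoprotein.

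**The concern.** The VTC definition needs an AE record, and 10.3.1 gives an investigator grounds not to make one. The protocol itself treats these events as progression: section 2.3.2 counts development of DME as progression of diabetic retinopathy, and section 4.2 describes PDR and DME as later stages. Nothing exempts VTCs from the exclusion. Whether a new PDR is worse than expected for that participant is left to each site, and Protocol 10.1.5 describes no committee that adjudicates VTCs.

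If some events go unrecorded, the event count falls and any absolute difference between arms shrinks. In a narrow set of cases a participant who should be a non-responder in the primary analysis could be counted as a responder.

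The censoring change works in the same direction. A participant kept in the risk set past the last informative examination can only leave the estimated event probability unchanged or lower it.

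**Working it through.** The plan gives no figure for VTC. Its one design figure, at least 90% probability of proof of concept with 40 evaluable per arm, reproduces as 0.903 and is not in question here.

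**Recording, component by component**

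- PDR: the SAP adds DRSS 61 or above, but inside the AE-based definition. It does not say which source prevails if the reading centre grades 61 and the site reports no AE. SAP Table 6-1 also carries level 90, which means the image cannot be graded; read literally, 61 or above would count that as PDR.
- Neovascularisation: abnormal slit-lamp findings go to medical history or AE, as applicable (Protocol 8.1.1.6).
- DME: new, clinically relevant OCT pathology is to be reported as an AE (Protocol 8.1.1.4), and OCT is done at every visit. This is the best-protected component.
- Acuity loss: BCVA is measured on schedule, so the event can be computed whether or not an AE is reported.

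**Size of under-recording (illustration only)**

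Let d be the share of VTCs that are counted only if an AE is reported, and u the fraction of those left unreported. Recorded risk = true risk × (1 − d × u). The documents give none of these quantities. Assume true 48-week risks of 20% on placebo and 10% on runcaciguat, with 46 and 52 randomized. With full recording, expected events are 46 × 0.20 + 52 × 0.10 = 9.2 + 5.2 = 14.4.

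| d | u | Factor | Expected events | Arm difference (points) |
|---|---|---|---|---|
| any | 0 | 1 | 14.4 | 10 |
| 0.5 | 0.25 | 0.875 | 12.6 | 8.75 |
| 0.5 | 0.50 | 0.75 | 10.8 | 7.5 |
| 1 | 0.25 | 0.75 | 10.8 | 7.5 |
| 1 | 0.50 | 0.50 | 7.2 | 5 |

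The d = 1 rows are a ceiling for each u, because they let acuity loss and OCT-detected DME go unrecorded too. If u is equal in the two arms, as masking makes plausible, the risk ratio is unchanged and only counts and absolute differences shrink.

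**Route to the primary endpoint (Protocol 9.4.2, SAP 4.2.2)**

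A missed VTC alters the result only if all of these hold: Week 48 DRSS is missing; the participant did not drop out before Visit 9, since such dropouts are non-responders anyway; and the carried-forward DRSS shows at least 2 steps of improvement.

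**Censoring (nominal days, Table 1-4)**

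Fundus photography and segment examination after baseline are scheduled only at Visits 9, 12 and 15 (days 85, 169 and 337).

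| Last visit | SAP censoring day | Last scheduled photograph | Gap in days |
|---|---|---|---|
| 10 | 113 | 85 | 28 |
| 11 | 141 | 85 | 56 |
| 13 | 225 | 169 | 56 |
| 14 | 281 | 169 | 281 − 169 = 112 |

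The gap is zero when the last visit is 9, 12 or 15.

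The effect on the estimate is small. Assume 46 placebo participants at risk after Visit 12, 5 of whom are last seen at Visit 14, and one VTC recorded at Visit 13. The step is 1/46 = 2.2% under the SAP. Under the protocol rule, if a photograph is required, it is 1/41 = 2.4%. With 9 such dropouts it is 1/37 = 2.7%.

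**The case against.** The best reply is that the specific rule governs the general one. Section 8.1.2 names these events as AEs. Section 10.3.1 excludes only progression that is no more severe than expected, and it also counts newly diagnosed conditions and exacerbations as AEs. OCT findings have their own reporting instruction. SAP 4.3.1.2 says VTCs are recorded continuously and separately by eye, which suggests dedicated capture. The eCRF is not available, so actual under-recording is unproven.

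This stands as far as it goes. A reader might infer that a site following 10.3.1 must leave out a new PDR; the text does not require that. What remains is that two sections can be read differently for the same event and neither document names the source that decides.

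On censoring, the reply is that the protocol never defines what shows the absence of an event. Visit 14 includes OCT and BCVA, so if any VTC examination suffices, the two rules agree there. They also agree when the early-discontinuation Visit 15 is done with full imaging, which Protocol 7.2 and SAP 4.1.4 request where possible. Both points are right. They narrow the effect but leave the dropped condition undeclared.

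A reader might also call VTC a key secondary endpoint, because Protocol 9.4 says its summary covers "the most important endpoints including primary and key secondary endpoints" and 9.4.3.1 then lists VTC. No passage gives VTC that label individually, and no decision rule uses it.

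**Conclusion.** Both inconsistencies are in the text and merit correction in the SAP. The first is a risk of site-dependent recording of a secondary endpoint, greatest for PDR and neovascularisation and least for acuity loss. The illustrated losses rest on assumed risks and assumed non-reporting and are not estimates for this trial.

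A reader might infer that any VTC makes a participant a non-responder, so that under-recording inflates the primary result generally. The documents do not support that: the rule applies only to a VTC before a missing assessment, and it matters only if the carried-forward DRSS shows response. No effect on the proof-of-concept decision has been shown.

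The second is an undeclared departure from the protocol. For a dropout last seen at Visit 14 it credits between 0 and 112 days without PDR assessment, depending on what counts as showing no event. It concerns only dropouts whose last visit lacked the full examination.

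**What to change.** Before unmasking, amend the SAP as follows.

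- Derive VTC from data already collected: reading-centre DRSS 61 to 85, with level 90 excluded; reading-centre centre-involved DME on OCT, with the on-study definition written out; recorded neovascularisation; and a BCVA loss of 10 letters or more from baseline. Keep AE reports as a supplementary source, for example for PDR found between photography visits.
- Restore the protocol's censoring condition and name the examinations that count as evidence of no event.

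No new assessment is needed. The cost is derivation and programming work, plus a definition of on-study DME, because the thickness thresholds in exclusion criterion 6 and Protocol 8.1.1.4 serve eligibility. Neovascularisation will still depend partly on what sites record.

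Reconcile Protocol 8.1.2 with 10.3.1 at the next protocol amendment, if there is one. That step needs ethics committee approval (Protocol 10.1.1) and would not by itself recover events already missed. Derivation from collected data can recover those that the reading-centre or acuity data show, which is why the SAP change comes first.

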8.1.3 Albuminuria

Albuminuria evaluations were removed from the protocol via Amendment 3.

8.1.4 Visual function questionnaire (VFQ-25)

VFQ-25 evaluations were removed from the protocol via Amendment 3.

8.2 Safety assessments

Planned time points for all safety assessments are provided in the SoA.

8.2.1 Physical examination

A physical examination (by means of inspection, palpation, auscultation) will be performed by a physician at the study site and will cover at least the organs of the cardiovascular, respiratory and abdominal systems. Measuring the body temperature will be included.

Abnormal physical examination findings are recorded either as medical history or as AEs in the eCRF.

Body weight will be measured by a member of the investigator's team under the following conditions:

- Participant in light clothing without shoes after having emptied the bladder
- Analogue or digital scale physician scale, measurement precision 0.1 kg

Height will be taken at screening only.

The BMI will be calculated by Data Management on the eCRF based on weight and height.

8.2.2 Vital signs

Pulse rate and systolic / diastolic blood pressure will be measured repeatedly pre-dose, and on the time points provided in the SoA (Section 1.3) after the initial dose and at steady state of each dose-level.

09 FEB 2023 Page: 52 of 95

Vital signs will be measured in a supine or semi-supine position after ≥ 5 minutes rest. Vital signs should always be measured before blood draws when scheduled at the same time point. Blood pressure and pulse rate measurements will be performed with a completely automated device.

